3.3.3. Dose Limiting Toxicity

Table 3 Dose-Limiting Toxicity Criteria

REVISED ROW

Toxicity	DLT Definition
Hematologic	
 Grade 4 absolute neutrophil count (ANC) for >7 days Febrile neutropenia (defined as concurrent Grade 4 neutropenia and fever >38.5°C and lasting >24 hrs) (according to CTCAE v.4.0 criteria) Grade 4 thrombocytopenia or anemia for > 7 days
Non-hematologic	
 Grade 3 or greater nausea, vomiting, or diarrhea that does not respond to standard medical care within 72-48 hours. Grade 3 or greater clinically significant non-hematologic toxicity per NCI-CTCAE, v 4.0

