3.8.4. Dose Adjustment For Hematologic Toxicity

3.8.4.1. For subjects with lymphoma and multiple myeloma:

The treatment may be held for 2 weeks if:

- ≤5% myeloblasts in bone marrow AND
- neutrophil and platelet count did not recover to neutrophils $\geq 0.5 \times 10^9/L$ and platelets $\geq 25 \times 10^9/L$

The treatment may resume as soon as count recovery has occurred (i.e., neutrophils ≥ 0.5 and platelets $\geq 25 \times 10^9/L$).

The treatment may be held for additional 1-2 weeks if the neutrophil and platelet count did not recover after 2 weeks.

When the treatment resumes, the dose may be adjusted based on platelet count, i.e., dose can be reduced by at least 25% increments up to twice when the platelet count $\leq 25 \times 10^9/L$ (G4 thrombocytopenia) and it is not attributed to the disease. If a subject has persistent G4 thrombocytopenia for 4 weeks not attributed to disease or requires platelet transfusions for bleeding in the absence of the disease, the subject will be withdrawn from the study.

3.8.4.2. For subjects with solid tumors:

- Grade 1 & 2 (platelet count \geq 50,000): Continue dosing at same dose level with weekly or more frequent monitoring as necessary

- Grade 3 (platelet count between 25,000 to <50,000): After discussion with medical monitor and using sound clinical judgement, continue at same dose or adjust dose (e.g. consider missing one dose or till count recovery to Grade 2). Monitor CBC at least twice a week, more frequently if necessary

- Grade 4 (platelet count below 25,000): Interrupt study medication and monitor CBC every 2-3 days. If platelet counts recover to Grade 2, discuss with medical monitor resuming treatment at the same or adjusted dose based on sound clinical judgement. Platelet transfusion is allowed based on institutional guidelines. In case of platelet transfusion, hold drug for at least 7 days from day of transfusion, and if platelet counts recover to Grade 2 consider initiating treatment at a lower dose using sound clinical judgement and after consulting with the GSK medical monitor. Discontinue treatment if drug has to be held for >14 days or greater than 2 dose reductions required.

Section 4: INVESTIGATIONAL PRODUCT

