- normal free light chain (FLC) ratio and
- absence of clonal cells in bone marrow by immunohistochemistry or 2-4 color flow cytometry.

CR (complete response):

- Negative serum and urine immunofixation, and
- Disappearance of any soft tissue plasmacytomas, and
- $\leq 5\%$ plasma cells in bone marrow.

VGPR (very good partial response):

- Serum and urine M-component detectable by immunofixation but not on electrophoresis OR
- 90% or greater reduction in serum M-component plus urine M-component $< 100\text{mg}/24\text{h}$.

PR (partial response):

- $\geq 50\%$ reduction of serum M-protein and reduction in 24 hour urinary M-protein by $\geq 90\%$ or to $< 200\text{mg}/24\text{h}$, and
- If the serum and urine M-protein are not measurable, a $\geq 50\%$ decrease in the difference between involved and uninvolved free light chain levels is required in place of the M-protein criteria. If serum and urine M-protein are not measurable, and serum free light chain assay is also not measurable, $\geq 50\%$ reduction in bone marrow plasma cells is required in place of M-protein, provided baseline bone marrow plasma cell percentage was $\geq 30\%$, and
- In addition to the above listed criteria, if present at baseline, a $\geq 50\%$ reduction in the size of the soft tissue plasmacytomas is also required.

MR (minimal response):

- $\geq 25\%$ but $\leq 49\%$ reduction of serum M-protein and reduction in 24 hour urinary M-protein by 50% to 89%, AND
- If present at baseline, 25% to 49% reduction in the size of soft tissue plasmacytomas is also required.
- No increase in size or number of lytic bone lesions (development of compression fracture does not exclude response).

SD (stable disease):

- Not meeting criteria for CR, VGPR, PR, MR or Progressive Disease.

Progressive Disease:

Requires any one or more of the following:

- Increase of $\geq 25\%$ from lowest response value in any one or more of the following:
 - serum M-component (absolute increase must be ≥ 0.5 g/dl), or
 - urine M-component (absolute increase must be ≥ 200 mg/24h), or
 - the difference between involved and unininvolved free light chain levels (absolute increase must be > 10 mg/dl): only for subjects without measurable serum and urine M-protein levels, or
 - bone marrow plasma cell percentage (the absolute % must be $\geq 10\%$) – only for subjects without measurable serum and urine M-protein levels and without measurable disease by FLC level.

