Vital signs	BP, body temperature, pulse rate, respirations Cycle 1 Day 1 vitals should be taken at same time points as PK draws on PK Table 7	X	X (Day 1 follow PK Table 7)	X	X	X	Prior to each infusion	X
ECG ^b	Pre-infusion and at the end of infusion except on Day 1 (Section 7.3.4). Two copies of the ECG tracing should be obtained at the time of the ECG, one to be kept in the study file for retrospective collection by the sponsor if necessary. ECG data should be reviewed by qualified personnel with experience in this study population	X	X ^b	X	X		On Day 4 of each cycle	X

STUDY PHASE	VISIT	SCREEN	First Treatment Period Cycle 1				Continuation Phase Cycle 2 and beyond	Follow- Up ⁱ	
			Day 1 and 4 ^a	Day 8 and 11 ^a	Day 15 and 18 ^a	Day 21			
			VISIT WINDOW (\pm days)	-14					
Holter Monitoring	Continuous 12-lead Holter ECGs (obtained via a Holter monitor) will be acquired for a total of approximately 24 hours beginning an hour before infusion on Day 1 only		X (Day 1)						
ECHO /MUGA	At Screening	X							
Concomitant medications	See Section 9.2 for list of prohibited and cautionary medications	X	X	X	X	X	continuous	X	
Adverse events (Refer to Section 8)	Adverse event assessment should be continuous	X	X	X	X	X	continuous	X	
Blood Sampling: on dosing days, collect blood samples prior to dosing unless otherwise noted									
Chemistry	No need to repeat at pre-dose Day 1 if screening assessments were performed within 72 hours of first dose (- 1 day visit window after screening)	X	X	X	X	X	Prior to every infusion	X	

	STUDY PHASE	SCREEN	First Treatment Period Cycle 1				Continuation Phase Cycle 2 and beyond	Follow- Up ^j
			Day 1 and 4 ^a	Day 8 and 11 ^a	Day 15 and 18 ^a	Day 21		
			VISIT	Screen	VISIT WINDOW (±days)	-14		
Hematology	No need to repeat at pre-dose Day 1 if screening assessments were performed within 72 hours of first dose (- 1 day visit window after screening)	X	X	X	X	X	Prior to every infusion	X
Coagulation	PT/PTT/INR. No need to repeat at pre-dose Day 1 if screening assessments were performed within 72 hours days of first dose(- 1 day visit window after screening)	X						
Blood sample for circulating biomarkers	A blood sample for circulating biomarkers should be obtained on Day 1 (prior to treatment), Day 21and at the time of disease progression		X			X		X (at progression)

	STUDY PHASE	SCREEN	First Treatment Period Cycle 1				Continuation Phase Cycle 2 and beyond	Follow- Up ⁱ
			Day 1 and 4 ^a	Day 8 and 11 ^a	Day 15 and 18 ^a	Day 21		

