G2	Continue dosing with no change OR Consider holding for up to 2 weeks for toxicity to resolve to baseline or \leq Grade 1, then continue at the same dose OR dose reduce by at least 25% to 1 dose level lower per dose escalation scheme if the toxicity is considered a DLT.
G3 and 4	Hold for up to 2 weeks for toxicity to resolve to baseline or \leq Grade 1, then dose reduce by at least 25% to 1 dose level lower per dose escalation scheme If no recovery to \leq Grade 1* or baseline after 14 days, patient should be withdrawn.

If the non-hematologic toxicity or event resolves to baseline or \leq Grade 1 within 14 days of stopping therapy, treatment with GSK2816126 may be restarted at 1 with at least 25% dose level lower than the current dose reduction. For a non-DLT, the treatment with GSK2816126 could restart at a full dose, if deemed appropriate.

If the non-hematologic toxicity does not resolve to \leq Grade 1 or baseline within 14 days, the subject should be withdrawn from the treatment permanently (Section 6.3). However, if the investigator and GSK Medical Monitor agree that further treatment will benefit the subject, treatment can restart with at least 25% dose reduction 1 dose level lower and under weekly clinical monitoring. If the toxicity resolves to \leq Grade 1 or baseline, the dose may be resumed to the initial dose level.

Section 3.8.4.1 For subjects with lymphoma and multiple myeloma:**REVISED TEXT**

When the treatment resumes, the dose may be adjusted based on platelet count, i.e., dose can be reduced by ~~at least 25% increments up to twice 1 or 2 dose levels~~ when the platelet count $\leq 25 \times 10^9/L$ (G4 thrombocytopenia) and it is not attributed to the disease. If a subject has persistent G4 thrombocytopenia for 4 weeks not attributed to disease or requires platelet transfusions for bleeding in the absence of the disease, the subject will be withdrawn from the study.

Section 3.8.4.2 For subjects with solid tumors:**REVISED TEXT**

- Grade 3 (platelet count between 25,000 to $<50,000$): After discussion with medical monitor and using sound clinical judgement, continue at same dose or ~~consider dose interruption until adjust dose (e.g. consider missing one dose or till count recovery to Grade 2 or less). Monitor platelet count CBC at least a minimum of twice a weekly, more frequently if necessary.~~

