- Grade 4 (platelet count below 25,000): Interrupt study medication and monitor ~~CBC platelet count~~ every 2-3 days. If platelet counts recover to Grade 2, discuss with medical monitor resuming treatment at the same or adjusted dose based on sound clinical judgement. Platelet transfusion is allowed based on institutional guidelines. In case of platelet transfusion, hold drug for at least 7 days from day of transfusion, and if platelet counts recover to Grade 2 consider initiating treatment at a lower dose using sound clinical judgement and after consulting with the GSK medical monitor. Discontinue treatment if drug has to be held for >14 days or greater than 2 dose reductions required.

Section 3.9.1 Dose Modifications**REVISED TEXT**

Dose reductions for GSK2816126 will depend on their starting dose. If a subject has a dose reduction for toxicity the dose will be reduced ~~by one dose level by a minimum of 25%~~. Approval from the GSK Medical Monitor is required to restart a dose after 14 days of dose interruption. Following a dose reduction subjects may be re-escalated to a higher dose level with the approval of the GSK Medical Monitor if the toxicity has resolved.

Section 5.1 Number of Subjects

Rationale for Change: updated total number of subjects to be enrolled based on added Part 1 expansion cohorts and revised subject numbers in Part 2.

REVISED TEXT

A maximum of approximately 250~~169~~ subjects will be enrolled. See Section 12.2 for sample size assumptions.

The number of dose levels and the level at which the RP2D (or MTD or MFD) is reached cannot be determined in advance. An adequate number of subjects will be enrolled into the study to establish the recommended dose(s) for further study. It is estimated that approximately 40 subjects will be enrolled into Part 1 dose-escalation of the study.

Additionally i-n Part 1 cohort expansion, approximately 27 GCB-DLBCL subjects and approximately 15 solid tumor subjects containing EZH2 inhibitor sensitizing mutations or subjects with prostate cancer will be enrolled.

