a.	A subject is to receive two doses per week which should be given with at least 2 non-dosing days in between on the same day of the week during Cycle 1 . 3 days apart . If there is a need to change scheduling after Cycle 1, the scheduled days of the week can change as long as there are 2-3-4 non-dosing days between doses ing days .												
b.	Timings for triplicate in-house on-drug ECGs are pre-infusion, at the end of infusion, before bed, and before discharge the next morning for Day 1 of cycle 1 only. Other protocol-mandated ECGs should be performed in triplicate pre-infusion and at the end of infusion (Section 7.3.4). Two copies of the ECG tracing should be obtained at the time of the ECG , one to be kept in the study file for retrospective collection by the sponsor if necessary . ECG data should be reviewed by qualified personnel with experience in this study population												
c.	Retention of screen-failure tumor tissue: all or a portion of archival or fresh biopsy tissue from screen-failure subjects, used for central testing of GCB-DLBCL or EZH2 mutation status, will be retained. This tissue may be used in the validation of potential diagnostic assays to detect EZH2 mutations and/or for GCB-DLBCL subtyping.												
d.	If the Follow-up visit \geq 842 weeks from the previous response scan time point, scans should be obtained to confirm/ evaluate response.												
e.	Standalone PET dose not replace CT. Diagnostic CT is the preferred method of disease assessment. PET/CT may be used as an alternative at the investigator's discretion.												
f.	Only if initially and/or previously positive & required for CR or as clinically indicated.												
g.	Whole Blood for Biomarker sample at Cycle 2 day 1 must be taken prior to start of dosing												
h.	If tissue sample not able to be taken at C1D18, site should discuss with GSK regarding having the sample taken at the next Cycle visit												
i.	Serum beta-human chorionic gonadotropin (B-HCG) pregnancy test												
j.	Follow up visit should be performed 30 days from last dose of study medication												

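### The two-week haematologic hold for lymphoma and myeloma depends on a marrow myeloblast percentage that the protocol never schedules and that does not measure these tumours

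*Protocol*

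**What the plan says.** Section 3.8.4.1 covers subjects with lymphoma and multiple myeloma. It permits a two-week hold on two joint conditions: "≤5% myeloblasts in bone marrow AND" failure of neutrophils and platelets to recover to at least 0.5 and 25 x 10^9/L. Dosing may resume once those counts are reached. A longer hold is then allowed on counts only: "The treatment may be held for additional 1-2 weeks if the neutrophil and platelet count did not recover after 2 weeks". Later in the section, dose reduction and withdrawal turn on Grade 4 thrombocytopenia that is not put down to the disease.

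The bullet stands in the record of sections added by the amendment before Amendment 4. Amendment 5 reprints one paragraph of Section 3.8.4.1, the one that begins "When the treatment resumes, the dose may be adjusted based on platelet count", and replaces percentage reductions with dose levels.

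**The concern.** A dose-hold rule has to be usable when the count comes back. Here the first condition calls for a marrow result that nothing in the schedule produces at that moment, expressed as a cell fraction the protocol does not otherwise ask anyone to report. Because myeloblasts are not the malignant cell in lymphoma or myeloma, the threshold also cannot do the one job a marrow condition might do, which is to tell drug-related from disease-related cytopenia.

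For the same severe cytopenia, one site might order or wait for a marrow before applying the stated hold, and another might ignore the bullet and hold on counts. Some subjects could have an unnecessary marrow procedure. Dose interruptions are listed among the Part 2 secondary safety endpoints, so uneven application would blur that summary.

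**Working it through.** The protocol states no figure to reproduce here. The check sets the rule beside the schedule and the neighbouring rules, then sizes the group it covers.

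**1. Is there a myeloblast assessment?** None is found in the text available. The laboratory list (Section 7.3.6, Table 8) gives a peripheral count with a five-part white-cell differential and no blast count. The myeloma response criteria (Appendix 6) use the percentage of "plasma cells in bone marrow".

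**2. Is any marrow sample tied to cytopenia?**

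| Disease | Marrow in the schedule | Source |
|---|---|---|
| Lymphoma | Baseline, within 35 days before treatment | Section 7.2 |
| Lymphoma, on treatment | "Only if initially and/or previously positive & required for CR or as clinically indicated" | Table 6, footnote f |
| Myeloma | Screening, Day 18, and Week 10 Day 1; required for non-secretory disease, otherwise as appropriate | Table 6 |

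No entry is triggered by a low count. The discretionary wording would allow a marrow, but nothing requires one, times one, or asks for a myeloblast readout.

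**3. Is it the relevant cell?** Section 1.1 places the lymphomas in the germinal-centre B-cell lineage, and myeloma is followed by plasma cells. The study design lists lymphomas, myeloma and solid tumours, with no myeloid leukaemia cohort.

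**4. What does the rule say in each case when counts have not recovered?**

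| Marrow myeloblasts | Stated two-week hold |
|---|---|
| 5% or less | Permitted |
| Above 5% | Rule silent |
| No current result | Cannot be shown to apply |

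In the schedule as written, the third row is the ordinary situation.

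**5. Do the neighbouring rules need a marrow?**
- Resumption and the further 1 to 2 weeks (Section 3.8.4.1): blood counts.
- Dose-limiting toxicity (Section 3.3.3, Table 3): for example "Grade 4 thrombocytopenia or anemia for > 7 days", with no marrow condition.
- Solid tumours (Section 3.8.4.2): "Grade 4 (platelet count below 25,000): Interrupt study medication and monitor" platelet counts, again with no marrow condition.

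So the shorter hold asks for more evidence than the longer one.

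**6. What is left if the bullet goes?** The remaining condition is failure to reach neutrophils of at least 0.5 and platelets of at least 25 x 10^9/L. The negation of (N ≥ 0.5 and P ≥ 25) is N < 0.5 or P < 25. Those counts are already available: Table 6 draws haematology at the Cycle 1 visits and, in later cycles, "Prior to every infusion".

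**7. Size.** Part 2 ceiling for lymphoma and myeloma (Section 5.1): 4 x 32 + 40 = 168. The protocol gives no incidence of counts this low, so a range of 5% to 20% is assumed:
- 0.05 x 168 = 8.4
- 0.20 x 168 = 33.6

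That is about 8 to 34 subjects. The 27 Part 1 GCB-DLBCL subjects are not added, because Section 3.4 counts those treated at the MTD/RP2D within Part 2. If Part 2 never opened, the same range on those 27 gives 0.05 x 27 = 1.35 to 0.20 x 27 = 5.4, about 1 to 5.

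**The case against.** There are four serious points on the other side.

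- **The operative text is not visible.** The bullet is seen only in an amendment record, and Amendment 5 says it corrected minor inconsistencies throughout, so an unlisted correction is possible. This stands as a limit on certainty. However, neither the Amendment 4 nor the Amendment 5 record removes the bullet, and Amendment 5 returned to this very section and listed a change to another paragraph only.
- **The rule is permissive.** It does not say that a hold is allowed only under these conditions. Section 3.9.1 contemplates interruptions and asks for Medical Monitor approval to restart after 14 days, and Section 6.3 tolerates delays of up to 21 days. This also stands, and it is why no claim is made that subjects must be dosed through cytopenia.
- **The condition would nearly always be met.** If myeloblasts are not the tumour cell, 5% or less should be the usual finding, so the bullet would seldom block a hold. That is fair as to the value, but showing that the condition is met still takes a marrow result the schedule does not provide.
- **Deletion leaves no attribution test on the hold.** One could instead name the relevant cell. But the myeloblast test never supplied attribution, and the existing disease-attribution wording for dose reduction and withdrawal would remain. Naming another cell would keep the need for a marrow sample at the time of cytopenia.

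It is also true that 8 to 34 counts everyone to whom the rule would apply. The number actually handled differently between sites would be smaller and cannot be estimated.

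**Conclusion.** The concern holds. As written, the first hold rests on an assessment that is undefined, untimed and aimed at the wrong cell, and it is out of line with the count-based rules around it. It should be corrected, but its reach is modest: it bears on consistent safety management and on the dose-interruption summary, not on response rate, stopping rules, sample size or error rates.

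The conclusion assumes that the bullet survives in the current body text, which cannot be confirmed from the part available. Confidence is therefore medium. The size rests on an assumed incidence and on Part 2 filling to its ceiling.

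**What to change.** Delete the myeloblast bullet from Section 3.8.4.1, so that the two-week hold depends only on neutrophils < 0.5 or platelets < 25 x 10^9/L. Keep the present wording on disease attribution for dose reduction and withdrawal, and add no marrow procedure. First confirm that the bullet is still in the current body of the protocol.

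The cost is one deleted bullet. No new assessment is needed, because the blood counts are already scheduled.

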4.1. Description of Investigational Product

Table 5 Investigational Product

REVISED ROW

Route/ Regimen	Delivered as an intravenous solution over 2 - 4 hours Study drug can be diluted into saline or dextrose for a final volume of 250ml at ambient temperature and normal room lighting up to 48 hours prior to infusion. PVH, PE and PA bags and tubing are all acceptable. Requires protection from light during administration.
---------------------------	---

Section 5: STUDY POPULATION

REVISED TEXT

5.1. Number of Subjects

A maximum of approximately 169 Approximately 100 subjects will be enrolled. See Section 12.4 for sample size assumptions.

The number of dose levels and the level at which the RP2D (or MTD or MFD) is reached cannot be determined in advance. An adequate number of subjects will be enrolled into the study to establish the recommended dose(s) for further study. It is estimated that 40 subjects will be enrolled into Part 1 (dose-escalation) of the study. Up to 60 129 subjects will be enrolled in Part 2 in five expansion cohorts: two GCB-DLBCL cohorts with up to 30 subjects from the EZH2 wild-type population, and up to 30 subjects from the EZH2 mutation positive population, and two tFL cohorts with up to 16 subjects from the EZH2 wild-type population and up to 16 subjects from the EZH2 mutation positive population and up to 37 subjects in the MM cohort. Additional subjects/cohorts may be enrolled to allow for evaluation of additional dose levels.

Section 5.2. Subject Selection Criteria

REVISED TEXT

5.2.1. Part 1 Inclusion Criteria

~~Specific information regarding warnings, precautions, contraindications, AEs, and other pertinent information on the GSK study treatment that may impact subject eligibility is provided in the IB and SPM [GlaxoSmithKline Document Number 2013N169204_00, 2013].~~

Inclusion criteria no 3:

Tumor type criteria:

- Relapsed/refractory NHL that meets one of the following criteria:
 - GCB-Diffuse large B cell lymphoma (DLBCL) or transformed follicular lymphoma relapsed after, or refractory to at least one prior chemotherapy regimen (e.g., rituximab, cyclophosphamide, doxorubicin, vincristine, prednisone [R-CHOP]) AND not a candidate for standard salvage regimens or autologous stem cell transplant (e.g., due to age, comorbid conditions or failure to respond to salvage chemotherapy). Local confirmation of lymphoma subtype (e.g. GCB-DLBCL) is allowed for enrollment but must be confirmed through central laboratory testing.
 - GCB-DLBCL or transformed FL relapsed after or refractory to at least two prior chemotherapy regimens

- Other NHLs that have failed at least one prior line of therapy.

- Relapsed and/or refractory MM that have failed prior standard therapy and for which there is no standard salvage regimen.
- Solid tumors (RECIST evaluable, with the exception of castrate resistant prostate cancer (CRPC)) at least one and not more than three standard of care chemotherapeutic regimens, or tumor for which there is no approved therapy, or for which standard therapy is refused.

Inclusion criteria no.4:

DLBCL and tFL: Availability of archival tissue, or willingness to undergo fresh biopsy for: confirmation of GCB-DLBCL status (DLBCL subjects); retrospective central testing of EZH2 mutation status (DLBCL and tFL subjects),

For all other tumor types: availability of archival tissue or fresh biopsies as applicable. DLBCL and tFL: Availability of archival tissue, or willingness to undergo fresh biopsy for: confirmation of GCB-DLBCL status (DLBCL subjects); retrospective central testing of EZH2 mutation status (DLBCL, and tFL subjects),
For all other tumor types: availability of either archival tissue or fresh biopsies

Part 1 Cohort Expansion Tumor Type

Inclusion Criteria no 9

Adequate organ system function as defined below:

System	LABORATORY VALUES
Hematologic	
ANC	≥1.2 x 10 ⁹ /L
Hemoglobin	≥9 g//dL
Platelets	≥75x 10 ⁹ /L
Platelets for Subjects with MM	≥ 50,000 (transfusion independent)
PT/INR and PTT	≤1.5 x ULN
Hepatic	
Albumin	≥2.5 g/dL
Total bilirubin	≤1.5 times ULN
AST and ALT	≤2.5 times ULN without liver metastases ≤5 times ULN if documented liver metastases
Renal	
Serum Creatinine	≤1.5 mg/dL or Calculate Creatinine Clearance ^{a,b} OR 24 hr urine Creatinine Clearance
Calculate Creatinine Clearance ^{a,b} OR 24 hr urine Creatinine Clearance	≥50 mL/min ≥50mL/min
Reproductive/Endocrine	
Testosterone	<50ng/dL (only for subjects with CRPC)

Cardiac	
Left Ventricular Ejection Fraction (LVEF)	≥LLN (minimum of 50% LVEF) by ECHO or MUGA ^c

Abbreviation(s): ANC, absolute neutrophil count; ALT, alanine aminotransferase; AST, aspartate aminotransferase; ECHO, echocardiogram; INR, international normalization ratio, MUGA, multigated (radionuclide) angiogram; PT, prothrombin time, PTT, partial thromboplastin time, ULN, upper limit of normal, LLN, lower limit of normal. Calculated by Cockcroft-Gault formula

6. For MM subjects, adequate renal function is defined as serum creatinine ≤ 2.5 mg/dL OR creatinine clearance (either calculated or obtained via 24 hr urine collection) ≥ 30 mL/min ECHO is the preferred method
7. ECHO is the preferred method

